To provide analgesia while reducing the use of opioids and their associated adverse effects, there are multiple distinct approaches to postoperative donor site pain control. Such methods including continuous subcutaneous local anesthetic, subcutaneous anesthetic injections, topical agents, wound dressings, and nonpharmacological strategies.² Based on a review performed by Sinha et al.², few evidenced based recommendations exist despite the significance of donor site pain in this patient population. Within the category of subcutaneous anesthetic injections, the most robust evidence supports the use of lidocaine with 1:500,000 epinephrine based on a randomized control trial conducted by Gacto et al.⁵ Other common agents used include ropivacaine and bupivacaine, but further studies are needed to make true evidence-based recommendations for their use. Additionally, while these traditional formulations may provide effective analgesia at the donor site, the duration of action is relatively short, lasting 12 hours or less.³

Liposomal bupivacaine (Exparel) is a prolonged release formulation that can extend the duration of donor site analgesia. According to Dissanaike et al.³, Exparel has been shown to provide postsurgical analgesia for up to 72 hours and reduce postsurgical opioid requirements when compared with Bupivacaine or placebo in multiple surgical settings. In the setting of STSG donor site pain, however, Exparel use has not been extensively described. We hypothesize that the use of Exparel at STSG donor sites will improve pain control compared to the current standard of care of lidocaine.

2. We hypothesize that use of liposomal bupivacaine (Exparel) will decrease post-operative pain at the donor site compared to the current standard of care, lidocaine, for split thickness skin grafting in patients with burn injuries. We have two specific aims.

- a. To identify whether pain is decreased in patients receiving Exparel injections post-operatively at STSG donor sites compared to patients receiving lidocaine injections as measured by pain scores.
- b. To determine if there is a reduction in post-operative opioid pain medication consumption in STSG patients receiving Exparel injections at the donor site compared to patients receiving lidocaine injections.

B. Background and Significance

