3. N/A

II. Research Plan and Design

- A. Study Objectives:** The objective of this study is to determine if use of liposomal bupivacaine (Exparel) decreases postoperative pain at the donor site compared to lidocaine for split thickness skin grafting in patients with burn injuries. In addition, we aim to identify if use of Exparel at the donor site for split thickness autografting decreases opioid pain medication consumption postoperatively compared to use of lidocaine at the donor site in patients with burn injuries.
- B. Study Type and Design:** This study will be a prospective, randomized controlled trial. Study subjects will be blinded to their randomization to avoid bias. The control group will undergo split thickness autografting using the standard protocol, involving injection of lidocaine with epinephrine at the donor site. The experimental group will undergo injection of liposomal bupivacaine (Exparel) at the time of harvest of the skin graft. Baseline pain levels will be obtained for all subjects using a validated pain assessment scale, the

Visual Analog Pain Scale. Postoperatively, time to first opioid pain medication (excluding immediate postoperative recovery from anesthesia), total opioid consumption on a daily basis, and donor site interval pain scores using a validated pain assessment scale will be obtained. The experimental group will then be compared to the control group to determine if there is a significant difference in pain levels, time to first opioid, and overall opioid consumption between the two groups.

C. Sample size, statistical methods, and power calculation

[figure not shown]
1. Patients will be randomized using a computerized random number generator with 1:1 randomization. Differences between groups will be assessed using Chi square test for categorical variables and Student's t test for two means. Confidence intervals will be calculated to 95% and a p value of less than 0.05 will be considered statistically significant.
2. Only subjects will be blinded to their randomization group. Study subject number will be linked to their randomization group. Blinding may be broken if the subject experiences an adverse reaction to the medication utilized for their group so that they are aware that they cannot receive the medication in the future.

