 - d. Post-operatively, subjects will recover from anesthesia. Once the subject returns to routine care following completion of recovery from surgery, time to first opioid medication will be recorded. The Visual Analog Pain scale will be used to assess donor site pain at set time intervals. This will occur for three total days. The scale will take approximately one minute to complete and is easily completed by non-English speaking subjects as it is a visual scale. Daily narcotic usage will be obtained from the medical record and will be measured in morphine equivalents. Length of stay will be evaluated from the medical record.
3. Harvesting of the split thickness autograft will be performed in the standard fashion as described above. Treatment of partial and full thickness burns with autografting is the standard of care for many patients with burn injuries. Postoperatively and preoperatively, patients will complete a validated pain assessment scale on a daily basis. Pain is routinely assessed as part of postoperative care and nursing management of patients. As part of the study, a pain scale will be used to specifically ask about pain related to the STSG donor site, whereas the pain scale is typically used to ask about global pain in patient care.
4. Split thickness autografts will be harvested from the anterior and lateral thigh of subjects. Harvested skin may be greater than the size of the recipient burn site. Excess skin will be disposed of. No tissue samples will be collected as part of this study.
5. Timeline:

F. Risk/benefit assessment:

1. Physical risk: Risks include potential adverse reaction to liposomal bupivacaine (Exparel) or lidocaine. Adverse reactions associated with liposomal bupivacaine have been shown to be equal in severity and frequency to those expected with the routine use of lidocaine according to the FDA approval for liposomal bupivacaine. Patients in both groups will be undergoing split thickness skin grafting and will be at risk for common surgical post-operative events, including bleeding, infection, and pain.

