7. N/A
8. N/A

B. Sample / Specimen Collection: N/A

C. Tissue Banking Considerations: N/A

D. Procedures to protect subject confidentiality: Patients will be identified by nursing staff as enrolled in the study to collect the post-operative pain scale assessments. Nursing staff are experienced in maintaining patient confidentiality as this is an expectation with all levels of care they provide. Following the data collection process, the study subjects will be deidentified to maintain their confidentiality.

E. Quality Assurance / Monitoring

1. Data that is collected will be self-reported from patients or collected as objective data from the medical record. No subjective assessments will be done by study team members. There is a chance that study subjects could intentionally falsify their pain scores for secondary gain, for example, to receive more narcotic pain medications. To limit this potential, we will not be including patients in the study who have ongoing opioid use for chronic pain or abuse prior to admission.
2. There are no plans for third party monitoring of this study.

V. Data Analysis and Reporting

- A. Statistical and Data Analysis:** Differences between groups will be assessed using Chi square test for categorical variables and Student's t test for two means. Confidence intervals will be calculated to 95% and a p value of less than 0.05 will be considered statistically significant. Final statistical analysis will be conducted by statistician. Interim analysis is planned for at the half way point of the study (20 patients completed). Interim statistically analysis will be conducted by Co-Investigators.
- B. Outcome:** We expect that the experimental group will have decreased pain scores compared to the control group. We estimate a 2 point difference in pain scores for the STSG donor site and that this difference will occur at 1, 2 and 3 days post-op. We expect that opioid consumption and time to first opioid dose will also be decreased in the study group. Our power analysis calculation based on pain score decrease aims to enroll 40 patients in the study and this is our anticipated study end point.
- C. Study results to participants:** Study subjects may submit a written request to receive study results after completion of the study. If requested, results will be mailed to the study subject after completion of data analysis.

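### Pain, overall opioid consumption and time to first opioid are each tested at p<0.05 with no formal primary outcome or testing order; under no effect, the chance of at least one false-positive difference is about 8–14%, about half of it in the drug's favour

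*Combined protocol and SAP*

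**What the plan says.** Section I.A.2 states one hypothesis, about donor-site pain, and then says "We have two specific aims": one on pain scores and one on post-operative opioid consumption. Section II.A repeats the pair. It begins "The objective of this study is to determine if use of liposomal bupivacaine (Exparel) decreases postoperative pain at the donor site" and continues "In addition, we aim to identify if use of Exparel at the donor site for split thickness autografting decreases opioid pain medication consumption".

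Section II.B adds time to first opioid and says the groups will be compared to "determine if there is a significant difference in pain levels, time to first opioid, and overall opioid consumption between the two groups".

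The method is the same short text in II.C.1 and V.A: "Differences between groups will be assessed using Chi square test for categorical variables and Student's t test for two means", and "a p value of less than 0.05 will be considered statistically significant". Neither section separates the outcomes. The sample size statements in II.C.3 and V.B rest on the pain score alone.

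No section calls an outcome primary or secondary, sets a testing order, divides or adjusts the 5%, or says what result would make the trial positive.

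**The concern.** The 5% threshold limits the error of one comparison. When three outcomes are each judged against it and none is set apart, the chance that at least one crosses by luck exceeds 5%.

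The practical risk is a trial that shows nothing on pain but has one opioid result below 0.05. With 50 patients (II.C.3) or 40 (V.B), and no power calculation for either opioid outcome, that is a realistic ending, and the plan has no rule for reporting it. Opioid consumption is a specific aim of its own in I.A.2, and I.C.2 and II.F.5 present less opioid use as a main benefit. Such a result could therefore easily be presented as an aim met, with a p value that understates how often this happens by chance.

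**Working it through.** **Inputs.** Three outcomes (II.B). Threshold 0.05 for each (II.C.1, V.A). Pain difference 2, SD 2.5, power 80%, 25 per group (II.C.3). Sidedness is not stated. I take it as two-sided, because II.C.1 says "Confidence intervals will be calculated to 95" per cent and II.B speaks of a difference. The correlation between outcomes is not given, so it is varied from 0 to 0.9.

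**Step 1: the plan's own figure.** Per group, n = 2 × (1.960 + 0.842)² × 2.5² / 2² = 2 × 7.85 × 6.25 / 4 = 24.5, so 25. This reproduces II.C.3 (the t-based solution is 25.5, so 26). The trial is thus sized for a single two-sided 5% test of pain, with no allowance for other tests.

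**Step 2: three independent outcomes, no effect on any.**

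- False difference in either direction: 1 − (1 − 0.05)³ = 1 − 0.8574 = 14.3%.
- False difference in the drug's favour: 1 − (1 − 0.025)³ = 1 − 0.9269 = 7.3%.

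**Step 3: correlated outcomes.** Three normal test statistics with a common correlation and zero mean, each rejected when |Z| > 1.96 (2 million simulated draws per correlation; the first row is the closed form from step 2).

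| Assumed correlation | At least one false difference, either direction | At least one in the drug's favour |
|---|---|---|
| 0 | 14.3% | 7.3% |
| 0.3 | 13.6% | 6.8% |
| 0.5 | 12.5% | 6.3% |
| 0.7 | 10.9% | 5.5% |
| 0.9 | 8.4% | 4.2% |
| One test only | 5% | 2.5% |

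**Step 4: only the two specific aims.** If time to first opioid is left out, the either-direction figure is 1 − 0.95² = 9.75% at correlation 0, 9.0% at 0.5 and 7.0% at 0.9. The excess does not depend on counting the third outcome.

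**Step 5: what is not counted.** V.B expects the pain difference on each of days 1, 2 and 3, and V.A plans an interim analysis with no adjustment. Both would add error and are separate issues. For scale, three daily pain tests plus the two opioid outcomes give about 16–21% in either direction (assuming correlation 0.5–0.8 between days and 0.2–0.5 otherwise). One unadjusted half-way look takes a single outcome from 5% to about 8.3%.

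**Step 6: effect of a fixed order.** If an opioid outcome can be claimed only after pain is significant, then under no effect a false claim requires a false positive on pain first. The overall chance returns to 5% in either direction and 2.5% in the drug's favour, for any correlation, given one pain measure and one look.

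**The case against.** The strongest reply is that the plan does have an order, though not a formal one. Pain is the only outcome in the hypothesis, the main objective with opioid use added to it, and the only basis for the sample size. Time to first opioid is in neither specific aim. A reader could treat pain as primary and the rest as supportive, and on that reading, with one pain measure and one look, the deciding test has a 5% error. This is right about intent, and it makes the remedy easy. But a power basis is not a decision rule, and nothing says how an opioid p<0.05 is to be read if pain fails.

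The correlation may also be high. Total opioid and time to first opioid come from the same medication record, so the lower end of the range is plausible. That is why the range runs to 0.9; even there the figure is above 5%.

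Three stronger readings are tempting, and the documents do not support them:

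- *An ineffective drug would win on some outcome 13–14% of the time.* With two-sided tests, 13–14% counts differences in either direction, including those favouring lidocaine, and needs a correlation of about 0.4 or less. It would describe false wins only if the tests were one-sided at 0.05 (14.3% at correlation 0, 13.1% at 0.3), which the plan does not say.
- *Any one significant opioid result makes the trial a success.* The plan defines when a comparison is significant, not when the trial succeeds.
- *Length of stay is a fourth test, giving about 18.5%.* II.E.2.d says "Length of stay will be evaluated from the medical record", but II.B does not list it for comparison and V.B states no expected result for it.

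**Conclusion.** The concern holds in moderate form. Three outcomes are compared at p<0.05 with no formal primary outcome, testing order or adjustment. Under no effect, the chance of at least one false-positive difference is about 8–14% rather than 5%, and of one favouring the drug about 4–7% rather than 2.5%. That is between 1.7 and 2.9 times the nominal level (8.4/5 and 14.3/5).

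These figures assume two-sided tests, one test per outcome, no interim look, approximately normal statistics and a common correlation between 0.9 and 0. A single pain comparison taken alone is not invalidated. What is missing is the rule that ties the opioid results to it.

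**What to change.** In V.A, with the matching text in II.C.1, state that:

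1. The primary outcome is donor-site pain, as one pre-specified measure (for example a single summary over days 1–3), tested at two-sided 0.05. Without a single measure, this step is not one test.
2. If it is significant, total 72-hour opioid in morphine equivalents is tested at two-sided 0.05.
3. If that is significant, time to first opioid is tested at two-sided 0.05. State which direction counts as benefit, since V.B expects this time to decrease.
4. Confirmatory claims stop at the first non-significant result. Later outcomes are still reported, with 95% intervals.
5. Daily opioid use and length of stay are reported descriptively with 95% intervals.

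This needs no more patients, and Appendix III already collects both opioid measures. Pain keeps the whole 0.05 and the power it was sized for, provided the interim look is dealt with separately. The downside is that an opioid benefit cannot be claimed as confirmed if pain is not significant.

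Bonferroni is an alternative (0.05/3 = 0.0167 each; overall 4.9% if independent), as is Holm. Either would allow an opioid claim without pain, but pain would no longer be assured the full 0.05 for which the trial was sized.

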Liposomal Bupivacaine Versus Lidocaine for Skin Graft Donor Site Pain

NCT03854344

13 Nov 2018

Version date: 11/13/18

Principal Investigator: [name]

Study Title: Prospective Study of Liposomal Bupivacaine for Pain Control of Split Thickness Skin Graft Donor Sites

Co- Investigator(s): [name]; [name]; [name]; [name], [name], BSN

I. Purpose, Background and Rationale

A. Aim and Hypotheses

1. Split-thickness skin grafts (STSG) play an integral role in the treatment of burn, traumatic, and chronic wounds.¹ Over 160,000 skin grafts are performed annually and are used to treat one of every three burn injuries.¹ During the procedure, a graft is taken from a remote area of healthy skin, commonly the proximal thigh, and transferred to the burn wound. Following STSG harvest, a wound remains at the donor site that will heal by re-epithelialization over the coming weeks.¹ Common complications of the donor site wound include excessive pain, impaired healing, and scarring.² In many cases, the donor site is more painful than the recipient site, and has been reported by patients to be one of the most distressing symptoms in the early postoperative period.² Opioids are a mainstay of treatment of post-surgical pain due to their potent analgesic effects.³ Opioid may be associated with adverse effects such as nausea, vomiting, constipation, urinary retention, and most seriously, respiratory depression.⁴ Chronic opioid use may also induce tolerance and result in hyperalgesia.³

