2. Study Procedures:
 - a. Enrolled subjects will be randomized to the control group or the experimental group. Preoperatively, subjects will complete a validated visual analog pain assessment scale to assess baseline pain levels. This is described in further detail below. Informed consent for study participation will be obtained by a team member preoperatively and informed consent for split thickness autografting will be obtained by a surgical team member. All questions will be answered and risk/benefits/alternatives will be explained in detail to the study subject. The subject will then be taken back to the operating room and anesthesia will be induced. The surgical timeout will occur verifying subject name, medical record number, planned operation, and surgical site. The subject will be prepped and draped in a sterile manner.
 - b. For the control group: The recipient burn site will be excised to healthy, bleeding tissue and the size of the defect will be measured. The anterior thigh will be marked to determine the size of the autograft. Tumescent solution with lidocaine and epinephrine will be injected using a needle or cannula at the donor site. A split thickness skin graft will be taken using a Zimmer dermatome. The skin graft will be applied to the recipient site and will be fixated in the standard fashion. The donor site and recipient site will then be dressed according to the preference of the attending physician. The patient will then awaken from anesthesia. This procedure will typically take between 60 to 120 minutes.
 - c. For the experimental group: The procedure described above will be identical to that performed to the control group with the following exceptions: Liposomal bupivacaine with plain bupivacaine diluted according to manufacturer recommendations will be infiltrated subcutaneously at the skin graft donor site prior to conclusion of the procedure. The procedure length will be unaffected.

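### The protocol is inconsistent about the experimental treatment: II.E.2.c read literally adds liposomal plus plain bupivacaine to the lidocaine tumescent, while the title, aims, II.A, II.B and II.K read as one drug per arm.

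*Combined protocol and SAP*

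**What the plan says.** II.E.2.b (control group) places this step before the dermatome harvest: "Tumescent solution with lidocaine and epinephrine will be injected using a needle or cannula at the donor site".

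II.E.2.c (experimental group) is defined by reference to that procedure: "The procedure described above will be identical to that performed to the control group with the following exceptions". The drug exception that follows is: "Liposomal bupivacaine with plain bupivacaine diluted according to manufacturer recommendations will be infiltrated subcutaneously at the skin graft donor site", to be done before the procedure ends. The only other statement there is that the length of the procedure does not change.

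The question is framed differently elsewhere:
- Title: "Liposomal Bupivacaine Versus Lidocaine for Skin Graft Donor Site Pain".
- I.A.2, aim a: "To identify whether pain is decreased in patients receiving Exparel injections post-operatively at STSG donor sites compared to patients receiving lidocaine injections".
- I.A.2, aim b, on opioid consumption: "STSG patients receiving Exparel injections at the donor site compared to patients receiving lidocaine injections".
- II.A, whether Exparel "decreases postoperative pain at the donor site compared to lidocaine for split thickness skin grafting".
- II.B gives the control arm lidocaine with epinephrine as the standard protocol. For the experimental arm it names Exparel only, injected when the graft is harvested.
- II.K describes the injection as one drug or the other, given by an attending burn surgeon or a designee.

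**The concern.** The procedure section and the sections that state the question describe different treatment contrasts, and each contrast supports a different conclusion.

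If the tumescent stays in both arms, a positive result shows the benefit of adding liposomal plus plain bupivacaine to lidocaine-epinephrine. It cannot support using Exparel instead of lidocaine, which is what the aims ask. If the tumescent is replaced, the result bears on the aims, but the arms then also differ in epinephrine at the donor site unless an epinephrine-only tumescent is specified.

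There is a practical side as well. Several kinds of operator may give the injections (II.K). One who works from II.B and one who works from II.E.2.c could treat experimental subjects differently, and the visible data form would not show it.

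The allergy instruction in II.D.3 and II.L.3 also presumes a single drug. If experimental subjects receive lidocaine and bupivacaine, it does not say which to record after a reaction.

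**Working it through.** **1. The plan's own figure.** II.C.3 gives 25 per group for a 2-point difference, SD 2.5 and 80% power. With two-sided alpha 0.05 (sidedness is assumed), n = 2 × (1.960 + 0.842)² × 2.5² / 2² = 2 × 7.85 × 1.5625 = 24.5, so 25. The exact t calculation gives 25.5, so 26. The figure reproduces and is not in dispute. The documents do not say whether the 2 points refer to adding or replacing, so clarifying the arms gives no determinate new sample size.

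**2. The arms side by side.**

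| At the donor site | Control (II.E.2.b) | Experimental, II.E.2.c read literally | Experimental, if replacement was meant |
|---|---|---|---|
| Lidocaine | yes | yes | no |
| Epinephrine | yes | yes | not stated |
| Liposomal bupivacaine | no | yes | yes |
| Plain bupivacaine | no | yes | yes (II.E.2.c; II.B names Exparel only) |
| Timing of bupivacaine | – | before the procedure ends | at harvest (II.B) |

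Under the literal reading, the arms differ only by the two forms of bupivacaine. Under replacement, they differ by bupivacaine against lidocaine, and possibly by epinephrine. Under neither reading is the contrast Exparel alone against lidocaine.

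**3. The two timings.** The tumescent comes before harvest. An injection before the end of the procedure is naturally a separate, later step. An injection at harvest could be the same step with a different drug. The timing therefore bears on which reading is right, and the two sections do not agree.

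**4. Which outcomes could be touched.** I.A gives traditional local anaesthetics 12 hours or less. V.B expects the pain difference at days 1, 2 and 3. If day 1 is about 24 hours after surgery (assumed), lidocaine has worn off before the first of these scores. Appendix III totals opioid over 72 hours, so lidocaine could act in at most 12/72 = 1/6 of that window. Time to first opioid starts at the end of recovery and may fall wholly inside the 12 hours. Plain bupivacaine also acts early in the experimental arm, so no size can be given for what lidocaine would add.

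**5. Number of subjects concerned.** With 1:1 allocation, the experimental arm is 50/2 = 25 (II.C.3) or 40/2 = 20 (V.B).

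**6. Whether the data would reveal what was given.** Appendix III shows 16 fields, and 0 name the donor-site local anaesthetic. The field for non-opioid adjunct medication could hold it but does not say so. One figure in the form is not shown.

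**The case against.** The strongest reply is that the protocol reads as one drug per arm almost everywhere, and that II.E.2.c merely lacks a phrase saying the tumescent is replaced. II.B, the section that defines the arms, pairs lidocaine-epinephrine with Exparel. II.K speaks of one drug or the other. II.C.2 refers to a single medication for each group, the allergy rule does the same, and II.F.1 and II.F.4 use either/or wording. This stands as evidence that replacement may have been intended. It does not supply the missing instruction, because no available section says that experimental subjects receive no lidocaine.

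II.E.3 might be cited for the opposite view: "Harvesting of the split thickness autograft will be performed in the standard fashion as described above", without separating the arms. That sentence concerns taking the graft and does not mention local anaesthetic, so it is weak evidence that the tumescent stays. The point does not rest on it.

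The consequence for the pain scores is also modest, as step 4 shows. Finally, the consent text is not in the public file and could describe what each arm receives. The operative record may also list the drugs given, even if the study form does not.

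**Conclusion.** The protocol contradicts itself on what the experimental arm receives, and as written the procedure does not match the stated question. The consequence lies in which conclusion a positive result would support. No numerical shift in any endpoint is claimed, and the sample size is unaffected. The ambiguity covers every experimental subject, 25 or 20 depending on which enrolment target applies.

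A reader might infer that the trial is in fact an add-on trial, or that experimental subjects did receive lidocaine. The documents do not support that. II.B and II.K point towards replacement, and nothing shows what was done in the operating room. Nor do they support a claim that day 1 to 3 pain scores are materially distorted.

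The conclusion assumes that no unseen text (consent pages, the figure in Appendix III) settles the question, and that day 1 means about 24 hours after surgery. The correction is desirable and cheap, and the point should not be ranked higher than that.

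**What to change.** State in II.E.2.c whether the experimental arm receives the lidocaine-epinephrine tumescent, and make the injection timing there agree with II.B. Then follow one of two routes.

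- **The tumescent stays.** Restate the title, the I.A hypothesis, aims a and b, II.A and II.B as liposomal plus plain bupivacaine added to lidocaine-epinephrine versus lidocaine-epinephrine alone. Extend the allergy rule in II.D.3 and II.L.3 to all local anaesthetics given, and adjust the either/or wording in II.F.1 and II.K to match. The procedure as written does not change. The cost is rewording in several sections and giving up any claim that Exparel can be used instead of lidocaine.
- **Replacement is intended.** Insert 'in place of the lidocaine tumescent' in II.E.2.c, state whether an epinephrine-only tumescent is used for harvest, and describe the experimental treatment throughout as liposomal plus plain bupivacaine. This keeps the question in the aims but changes how the donor site is prepared relative to the literal text. The title of reference 5 concerns the haemostatic effect of adrenaline-lidocaine at donor sites, so the clinicians must agree how bleeding is handled.

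In either case, add one Appendix III field recording the local anaesthetics given at the donor site.
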